6.2 IMPORTANT PROTOCOL DEVIATIONS

Data discrepancies and deviations from the CTP will be identified for all patients in the database (i.e., enrolled patients). Consistency check listings (for identification of violations of time windows) and a list of protocol deviations will be provided to be discussed at the RPM/DBLM/MQRM. At this meeting, it will be decided whether a discrepant data value can be used in analyses or whether it must be queried in the clinical database. Each protocol deviation must be assessed to determine whether it is an important Protocol Deviation (iPD). For definition of iPDs, and for the process of identification of these, refer to the BI reference document "Identify and Manage Important Protocol Deviations (iPD)" (2).

If any iPDs are identified, they are to be summarised into categories and will be captured in the RPM/DBLM/MQRM minutes via an accompanying Excel spreadsheet (3). The following table contains the categories which are considered to be iPDs in this trial. If the data show other iPDs, for example, based on monitor visits to the sites, then this table will be supplemented accordingly by the time of the RPM/DBLM/MQRM. Not all iPDs will lead to exclusion from analysis sets. IPDs leading to exclusion from analysis sets are indicated as such in [Table 6.2: 1](#). IPDs will be summarised and listed for the randomized set.

IPDs will be summarized and listed for the randomized set.

Table 6.2: 1 Important protocol deviations

Category / Code	Description	Comments	Excluded from ¹
A	Entrance criteria violated		
A1	Inclusion criteria not met		
A1.01	Palmoplantar Pustulosis defined as presence of primary, persistent (>3 months duration), sterile, macroscopically visible pustules on the palms and/or soles, without or with plaque psoriasis elsewhere on the body. LABEL: No presence of PPP.	IC02 Also check versus PPP ASI that pustule severity > 0 on at least one region	PPS
A1.02	Presence of white or yellow pustules on palms and/or soles at screening and baseline LABEL: No presence of white or yellow pustules on palms/soles.	IC03	PPS
A1.03	Pustular severity score ≥ 2 in at least one region and ≥ 10 well-demarcated pustules (white or yellow pustules) across all regions at screening and baseline LABEL: No pustular severity score ≥ 2 in any region or <10 well-demarcated pustules	IC04 Also check versus PPP ASI that pustule severity ≥ 2 on at least one region	PPS
A1.04	PPP PGA of at least moderate severity (≥ 3) at screening and baseline. LABEL: PPP PGA not at least moderate severity	IC05. Also check versus reported PPP PGA at baseline.	PPS
A1.05	A minimum PPP ASI score of 12 at screening and baseline LABEL: PPP ASI < 12	IC06. Also check versus derived PPP ASI at baseline.	PPS

Table 6.2: 1 (cont'd) Important protocol deviations

Category / Code	Description	Comments	Excluded from ¹
A1.06	Male or female patients. Women of childbearing potential (WOCBP) must be ready and able to use highly effective methods of birth control per ICH M3 (R2) that result in a low failure rate of less than 1% per year when used consistently and correctly.	IC07	None
	LABEL: Contraception methods not used.		
A2	Exclusion criteria violated General Exclusion Criteria		
A2.01	Reduction in PPP ASI total score ≥ 5 from screening visit (Visit 1) to baseline (randomisation visit, Visit 2).	EC01 Also check versus PPP ASI at V1 and V2.	PPS
	LABEL: Reduction in PPP ASI total score ≥ 5 from V1 to V2		
A2.02	Patients with plaque psoriasis with worsening of plaque psoriasis within the last 3 months prior to screening.	EC02	PPS
	LABEL: Worsening of plaque psoriasis within the last 3 months		
A2.03	Skin conditions that affect ability to score area and severity of PPP components	EC03	PPS
	LABEL: No ability to score are and severity of PPP components		
A2.04	Women who are pregnant, nursing, or who plan to become pregnant while in the trial.	EC04	None
	LABEL: Pregnant or nursing.		

Table 6.2: 1 (cont'd) Important protocol deviations

Category / Code	Description	Comments	Excluded from ¹
A2.05	Severe, progressive, or uncontrolled renal, hepatic, haematological, endocrine, pulmonary, cardiac, neurologic, cerebral, or psychiatric disease, or signs and symptoms thereof. LABEL: Severe or uncontrolled disease.	EC05	None
A2.06	Presence or known history of anti-TNF-induced PPP-like disease. LABEL: Anti-TNF-induced PPP-like disease.	EC06	PPS
A2.07	Patient with a transplanted organ or who have ever received stem cell therapy LABEL: A transplanted organ or a stem cell therapy	EC07	None
A2.08	Known history of lymphoproliferative disease, including lymphoma, or signs and symptoms suggestive of possible lymphoproliferative disease, such as lymphadenopathy and/or splenomegaly. LABEL: Lymphoproliferative disease.	EC08	None
A2.09	Any documented active or suspected malignancy or history of malignancy within 5 years prior to screening, except appropriately treated basal cell carcinoma of the skin, squamous cell carcinoma of the skin or in situ carcinoma of uterine cervix. LABEL: Malignancy within last 5 years.	EC09	None

Table 6.2: 1 (cont'd) Important protocol deviations

Category / Code	Description	Comments	Excluded from ¹
A2.10	Use of any restricted medication as specified in CTP Table 4.2.2.1: 1_or any drug considered likely to interfere with the safe conduct of the study, as assessed by the investigator	EC10 – based on tick box only.	PPS
	LABEL: Use of restricted medication interfering safety		
A2.11	Administration of live vaccines during the study period or within 6 weeks prior to randomisation.	EC11	None
	LABEL: Live vaccine within last 6 weeks.		
A2.12	History of allergy/hypersensitivity to the systemically administered trial medication agent or its excipients.	EC12	None
	LABEL: History of allergy/hypersensitivity.		
A2.13	Active systemic infections during the last 2 weeks (exception: common cold) prior to randomisation, as assessed by the investigator.	EC13	None
	LABEL: Systemic infections within last 2 weeks.		
A2.14	Chronic or relevant acute infections including human immunodeficiency virus (HIV), viral hepatitis and (or) active or latent tuberculosis (TB):	EC14	None
	LABEL: Chronic or relevant acute infections.		
A2.15	Major surgery performed within 12 weeks prior to randomisation or planned within 52 weeks after randomisation, as assessed by the investigator.	EC15	None
	LABEL: Recent or planned major surgery.		

Table 6.2: 1 (cont'd) Important protocol deviations

Category / Code	Description	Comments	Excluded from ¹
A2.16	Patient has received surgical treatment of focal infection (e.g. tonsillectomy or dental therapy) within 6 months of randomisation. LABEL: Surgical treatment of focal infection	EC16	None
A2.17	Total white blood count (WBC) < 3,000/μL, or platelets < 100,000/μL or neutrophils < 1,500/μL, or hemoglobin <8.5 g/dL at screening. LABEL: WBC, PLAT, NEU, HGB below limit.	EC17 Also check versus screen Lab values	None
A2.18	Aspartate aminotransferase (AST) or alanine aminotransferase (ALT) > 2x the upper limit of normal, or total bilirubin > 1.5x the upper limit of normal (patients with Gilbert's syndrome are not excluded) at screening. LABEL: AST/ALT/TBIL above limits.	EC18 Also check versus screen Lab values (medical review for Gilbert Syndrome)	None
A2.19	Currently enrolled in another investigational device or drug study, or less than 30 days since ending another investigational device or drug study(s), or receiving other investigational treatment(s). LABEL: Recent enrollment in other study.	EC19	PPS

Table 6.2: 1 (cont'd) Important protocol deviations

Category / Code	Description	Comments	Excluded from ¹
A2.20	Chronic alcohol or drug abuse or any condition that, in the investigator's opinion, makes the patient an unreliable trial participant or unlikely to complete the trial. LABEL: Alcohol or drug abuse.	EC20	PPS
A2.21	Patients not expected to comply with the protocol requirements or not expected to complete the trial as scheduled. LABEL: No expectation to comply with the CTP or complete the trial.	EC21	PPS
A2.22	Previous randomisation in this trial. LABEL: Previous randomisation in this trial.	EC22	PPS
B	Informed consent		
B1	Informed consent not available LABEL: IC not available.	IC01 Date of informed consent missing or no signature on patient's "Declaration of Informed Consent" In this case: Patient's data will not be used at all.	All #
B2	Informed consent too late LABEL: IC too late.	IC01 Informed consent date was after Visit 1	None

Table 6.2: 1 (cont'd) Important protocol deviations

Category / Code	Description	Comments	Excluded from ¹	
C	Trial medication and randomisation			
C1	Incorrect trial medication			
C1.01	Study drug medication not taken at all LABEL: Study drug medication not taken at all.		All except for ES and RS	
C1.02a	Patient skipped an intermediate dose prior to Week 16 for other reason (all injections at one planned visit) LABEL: Patient skipped an intermediate dose prior to Week 16 for other reason.	Patient missing a dose at an intermediate visit when dose at a later scheduled visit has been taken due to other reason.	PPS	
C1.02b	Patient skipped an intermediate dose prior to Week 16 due to COVID 19 (all injections at one planned visit) LABEL: Patient skipped an intermediate dose prior to Week 16 due to COVID 19.	Patient missing a dose at an intermediate visit when dose at a later scheduled visit has been taken due to COVID 19.	PPS	#
C1.03a	Patient skipped an intermediate dose at or after Week 16 for other reason (all injections at one planned visit) LABEL: Patient skipped an intermediate dose at or after Week 16 for other reason.	Patient missing a dose at an intermediate visit when dose at a later scheduled visit has been taken due to other reason.	None	
C1.03b	Patient skipped an intermediate dose at or after Week 16 due to COVID 19 (all injections at one planned visit) LABEL: Patient skipped an intermediate dose at or after Week 16 due to COVID 19.	Patient missing a dose at an intermediate visit when dose at a later scheduled visit has been taken due to COVID 19.	None	#

Table 6.2: 1 (cont'd) Important protocol deviations

Category / Code	Description	Comments	Excluded from ¹	
C2	Incorrect Dosing			
C2.01	Incorrect medication received prior to Week 16 LABEL: Incorrect dose received prior to Week 16	Randomized patient who didn't receive correct planned total dose at any scheduled visit prior to Week 16. Can only be finally judged after DBL since unblinding information is required	PPS	
C2.02	Incorrect medication received at or after Week 16 LABEL: Incorrect dose received at or after Week 16	Randomized patient who didn't receive correct planned total dose at any scheduled visit at or after Week 16 Can only be finally judged after DBL since unblinding information is required	None	
C3	Randomization not followed			
C3.01	Treated without randomisation LABEL: Treated without randomisation.	Patient treated according to eCRF, but not randomised according to IVRS.	All	
C3.02	Randomization order not followed LABEL: Stratification error	Stratification error Programming check and also manual review after DBL	None	#
C4	Medication code broken			
C4.01	Medication code broken before week 16 without just cause LABEL: Code broken early without just cause.	Medication code was broken prior to DBL for the week 16 analysis for no valid reason. Final decision at the DBL meeting for the Week 16 analysis based on medical judgment.	PPS	#

Table 6.2: 1 (cont'd) Important protocol deviations

Category / Code	Description	Comments	Excluded from ¹	
C4.02	Medication code broken after week 16 without just cause	Medication code was broken after DBL for the week 16 analysis for no valid reason.	None	#
	LABEL: Code broken late without just cause.	Final decision at final DBL based on medical judgment.		
D	Concomitant medication			
D1	Previous medication			
D1.01	Washout of previous medication too short		PPS	#
	LABEL: Washout too short.			
D2	Prohibited medication use			
D2.01a	Use of restricted medication as per CTP Table 4.2.2.1: 1 on or after Screening or during the on-treatment period - when not provided as a rescue therapy to treat a worsening disease condition – prior to Week 16 primary analysis for other reason		PPS	#
	LABEL:# Restricted medication prior to week 16 primary analysis for other reason.			
D2.01b	Use of restricted medication as per CTP Table 4.2.2.1: 1 on or after Screening or during the on-treatment period - when not provided as a rescue therapy to treat a worsening disease condition – prior to Week 16 primary analysis due to COVID 19		PPS	#
	LABEL: Restricted medication prior to week 16 primary analysis for COVID 19.			

Table 6.2: 1 (cont'd) Important protocol deviations

Category / Code	Description	Comments	Excluded from ¹	
D2.02a	Use of restricted medication as per CTP Table 4.2.2.1: 1 on or after Screening or during the on-treatment period - when not provided as a rescue therapy to treat a worsening disease condition – after Week 16 primary analysis for other reason LABEL: Restricted medication after week 16 primary analysis for other reason.		None	#
D2.02b	Use of restricted medication as per CTP Table 4.2.2.1: 1 on or after Screening or during the on-treatment period - when not provided as a rescue therapy to treat a worsening disease condition – after Week 16 primary analysis due to COVID 19 LABEL: Restricted medication after week 16 primary analysis due to COVID 19.		None	#
E	Missing data	<not specified>		
F	Study specific analysis	<not specified>		
G	Other safety related deviations			
G1.01	Pregnancy test not done for woman of child bearing potential before IMP administration LABEL: Pregnancy test not done.	Pregnancy test not done at any visit before IMP was given.	None	#

PD will be detected manually;

Source: BI reference document 'Identify and Manage Important Protocol Deviations (iPD)' [001-MCS-50-413] (2.6).

¹ See Section 6.3 for population definitions

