4.1.3 Method of assigning patients to treatment groups

After the assessment of all in- and exclusion criteria, each eligible patient will be randomised to blinded treatment arms according to a randomisation plan in a 2:1:1:1:2 ratio at Visit 2 via Interactive Response Technology (IRT). This randomisation will be stratified according to region (i.e. Japan vs non-Japan).

Note that the medication number is different from the patient number (the latter is generated during screening via the IRT system). Each syringe will have an individual medication number for dispensation.

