4.1.4 Drug assignment and administration of doses for each patient

Study drugs will be administered subcutaneously. Injections will be given in a double blind fashion.

At randomisation as well as at subsequent medication dispensation visits, IRT will assign medication numbers. Site personnel will enter the medication numbers in the eCRF.

BI 655130 will be administered as a subcutaneous injection by the investigator or authorized study personnel. The date and time of the administration will be recorded in the eCRF. Details are described in the drug administration manual located in ISF.

[figure not shown]
The injection sites should avoid sites of psoriasis involvement as well as sites where the skin is tender, bruised, erythematous, or indurated, and should be alternated to other areas for subsequent doses.

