4.1.5 Blinding and procedures for unblinding

4.1.5.1 Blinding

Patients and investigators involved in the trial conduct will remain blinded with regard to the randomised treatment assignments until after database lock for the final trial analysis.

To maintain the treatment blind during the trial, all patients will receive 4 injections at all dosing visits in the every 4 weeks schedule, as indicated in the [Flow Chart](#).

The primary analysis of the trial will be performed once all randomised patients have completed through 16 weeks of trial treatment. At this time, a database lock for the primary analysis will be done and treatment will be unblinded. In order to confirm the integrity of the treatment blind while the trial continues through to completion, a logistics plan will be developed to describe the mechanisms that are to be put in place to assure that the patients and investigators remain blinded to both individual patient data, as well to the primary analysis results. The blind status of trial and project team members at this time will also be clarified. The logistics plan will be finalized prior to the treatment unblind for the primary analysis.

The access to the randomisation code will be kept restricted until its release at the time of the final trial analysis once all patients have completed the trial.

A fully independent DMC will perform an un-blinded safety and efficacy assessment at specified intervals in order to ensure that patients are protected from potential harm, please refer to [Section 8.7](#) for further details.

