7.2 PLANNED ANALYSES

7.2.1 General considerations

There will be 3 main patient populations in this trial for analyses: the full analysis set (FAS), the safety analysis set (SAF), and the per-protocol set (PPS).

Safety Analysis Set (SAF)

This patient set includes all patients who were randomised and received at least one dose of study drug. It will be the main analysis set for presentation of safety. Patients will be analyzed according to the actual treatment.

Full Analysis Set (FAS)

This patient set includes all patients in the SAF who had a baseline for the primary efficacy endpoint. Treatment assignment will be as randomised. This is the main analysis set for presentation of efficacy data.

Per-Protocol Set (PPS)

This patient set includes all patients in the FAS who adhered to the CTP without any IPDs (potentially affecting the study outcome) which lead to exclusion from the PPS. This set will be used for sensitivity analysis on the primary efficacy endpoint. Important deviations of the protocol will include violations of the key inclusion and exclusion criteria, incorrect medications taken, concomitant use of restricted medications, and any other deviations of the protocol deemed important by the study team. All decisions concerning important protocol deviations will be made prior to un-blinding of the database for the primary endpoint analysis at week 16, and a full list of such deviations will be provided in the trial Integrated Quality and Risk Management Plan (IQRMP).

Further analysis sets, [REDACTED], will be defined in the Trial Statistical Analysis Plan (TSAP).

Standard statistical parameters (number of non-missing values, mean, standard deviation (SD), median, quartiles, minimum and maximum) or frequency tables (including patient frequencies and percentages) will be calculated where appropriate.

The following analyses of this trial protocol, in chronological order, are planned:

Week 16 Primary Analysis

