For the primary analysis the dose-response relationship will be modeled using the total doses. Here, the total is the sum of all doses administered to the patient prior to the week 16 visit including both loading and maintenance phase. Thereby, it is assumed that the cumulative concentrations over time (AUC) and thus the cumulative total dose is the key driver of the efficacy response in the modelling part of MCPMod. [Table 7.4: 1](#) shows the calculated total doses per treatment arm.

Table 7.4: 1 Total dose per treatment arm.

High dose regime (Arm 1)	
Medium-high dose regime (Arm 2)	
Medium-low dose regime (Arm 3)	
Low dose regime (Arm 4)	
Placebo (Arm 5)	

W: Week.

The multiple comparison procedure will then be implemented using optimal contrast tests which control the family-wise type I error rate at a one-sided $\alpha = 0.05$. For the MCPMod test, the optimal contrasts of each candidate model are calculated using the R-function `optCont` using weights (w) proportional to the sample size of each dose group, respectively, and are shown in [Table 7.4: 2](#).

Table 7.4: 2 Contrast coefficient.

Model	Contrast coefficients for (total) dose				
	Placebo	Low dose: ██████████	Medium-low dose: ██████████	Medium-high dose: ██████████	High dose: ██████████
Linear	0.783	0.049	-0.049	-0.196	-0.587
Emax	0.869	-0.112	-0.151	-0.190	-0.416
Exponential	0.574	0.194	0.118	-0.106	-0.780
Logistic	0.706	0.220	-0.036	-0.279	-0.612
Sigmoid Emax	0.638	0.247	0.052	-0.256	-0.681

BI: Spesolimab total dose, ██████████ administered before week 16.

For the final evaluation, these contrasts will be updated using the expected model means from the candidate set and the estimated variance-covariance matrix extracted from the MMRM model. The updated contrast coefficients will be reported in the CTR.

Once the significance of a dose-response signal is established, the dose-response profile and the target dose can be estimated using a model averaging approach. Here, the final model is

derived as a weighted average over all significant model shapes. Here, the weights for each significant model (M_k) are given by

$$w(M_k) = \frac{\exp(0.5 \cdot AIC(M_k))}{\sum_{i=1}^K \exp(0.5 \cdot AIC(M_i))}$$

where $AIC(M_k)$ is the Akaike Information Criterion (AIC) of model M_k .

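### SAP C2.01 settles a per-protocol exclusion after unblinding, contrary to the protocol, and on its most natural reading partial under-dosing can exclude active-arm patients but not placebo patients

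*SAP*

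**What the plan says.** Protocol 7.2.1, in defining the PPS, fixes the timing: "All decisions concerning important protocol deviations will be made prior to un-blinding of the database for the primary endpoint analysis at week 16". Protocol 4.1.5.1 ties the Week 16 lock to unblinding: "At this time, a database lock for the primary analysis will be done and treatment will be unblinded".

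SAP Table 6.2: 1 (Section 6.2) flags C2.01 for exclusion from the PPS. The criterion covers a randomised patient whose total dose was not as planned "at any scheduled visit prior to Week 16. Can only be finally judged after DBL since unblinding information is required". The row is titled as incorrect medication and labelled as incorrect dose. The table does not say whether the planned total is counted in syringes or in drug.

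C1.02a and C1.02b, in the same table, exclude from the PPS a patient in any arm who misses all injections at a visit before Week 16 and takes a later dose. SAP 6.3 gives the PPS one role, a sensitivity analysis of the primary endpoint. SAP Section 4 lists two departures from the protocol, both about visits in the MMRM.

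**The concern.** There are two problems. The first is timing. A rule that decides who is in an efficacy set is finally judged once treatment codes are available, although the protocol rules this out. The SAP neither acknowledges nor justifies the departure.

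The second is what the rule measures. If the planned total means milligrams of spesolimab, the plan for placebo before Week 16 is zero, and missing a syringe leaves it at zero. The same lapse in an active arm changes the dose if that syringe held drug. Membership of the PPS then depends on treatment as well as on adherence.

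A per-protocol analysis is meant to show whether the primary result survives removal of patients with important deviations. If incompletely dosed patients do worse for reasons unrelated to the drug, removing them from the active arms while keeping them on placebo moves the comparison towards active. It then no longer tests robustness cleanly.

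**Working it through.** No figure in the plan depends on C2.01. As a check on the design inputs used below, a simulation of the linear 30-point scenario with a 25-point delta gave 76.0% success, against 77.1% in Protocol Table 7.5: 1.

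**Step 1: timing.**
- Protocol 7.2.1: all important-deviation decisions come before the Week 16 unblinding.
- Protocol 4.1.5.1: lock and unblinding happen together.
- C2.01: final judgement comes after lock and uses unblinding information.
- SAP Section 4: not listed as a change.

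The first and third statements cannot both be followed. C2.02 and C3.02 also involve work after lock, but neither leads to exclusion from any set. C4.01 does lead to PPS exclusion, and is decided at the lock meeting. C2.01 is the only PPS-exclusion row expressly deferred until after lock.

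**Step 2: what the planned total means.**
- Syringes injected are recorded in the eCRF, and SAP 7.3 already computes compliance as syringes injected over syringes planned. That needs no codes.
- C2.01 says codes are needed, so drug content must enter the test.
- SAP 7.4 uses total dose for the quantity on the dose axis: "the total is the sum of all doses administered to the patient prior to the week 16 visit including both loading and maintenance phase".
- SAP 6.3 handles misallocation of placebo patients by whether a spesolimab syringe was received.

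Drug amount is therefore the most natural reading, though not a stated definition.

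**Step 3: who is excluded on that reading.**

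| Event before Week 16 | Active arm | Placebo |
|---|---|---|
| Whole intermediate visit skipped, later dose taken | Excluded (C1.02a/b) | Excluded (C1.02a/b) |
| Some syringes missed at an attended visit | Excluded if a missed syringe held drug | Not excluded |
| Active drug given in error to a placebo patient | Not applicable | Excluded (C2.01) |

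The arm-dependent case is the second row.

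**Step 4: size, under assumptions.** Let q be the share of patients in each arm who are partially under-dosed, and D their outcome deficit in points of % PPP ASI change, unrelated to drug. If the other patients in an arm have mean m, the whole arm has mean (1 - q)m + q(m + D) = m + qD. Removing the under-dosed patients moves that arm by qD. Doing so in the active arms only shifts the active-placebo difference by qD.

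Neither q nor D is in the documents. Taking q = 2-15% and D = 10-20 points:

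| q | Active removed (of 100) | Placebo removed (of 40) | Shift, D = 10 | Shift, D = 20 |
|---|---|---|---|---|
| 2% | 2 | 0 | 0.2 | 0.4 |
| 5% | 5 | 0 | 0.5 | 1.0 |
| 10% | 10 | 0 | 1.0 | 2.0 |
| 15% | 15 | 0 | 1.5 | 3.0 |

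The table assumes that every under-dosed active patient missed at least one drug-containing syringe. Syringe make-up by arm is redacted, so for any given q and D these are upper bounds.

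**Step 5: scale.** With SD 35 and 40 patients per arm (Protocol 7.5), the high-dose versus placebo standard error is 35 x sqrt(1/40 + 1/40) = 7.8 points. The largest shift is 3.0/7.8 = 0.38 standard errors, and 3.0/20 = 15% of the 20-point benefit required in Protocol Section 7.

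**The case against.** The best defence is that C2.01 is a wrong-medication rule. Its title and label concern what was received, and only the code can show that a syringe held the wrong content. A rule covering both count and content would also need codes. Judging it finally after lock leaves room for a blinded first review, and the criterion and its consequence were written down in advance. The set it affects is one of several sensitivity analyses.

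Much of this stands. The drug-amount reading is inferred, and discretion after unblinding is limited, so a reader who pictures exclusions chosen freely with codes in hand goes too far. But a pure wrong-content reading does not remove the timing conflict. An undefined central term also leaves something to interpret at that point.

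Two stronger inferences are tempting and not supported:

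- **The PPS drops poor compliers from the active arms only.** C1.02a/b remove whole-visit skippers in every arm, and a placebo patient given active drug fails C2.01.
- **Active patients who stop treatment early are excluded while placebo stoppers are kept.** C2.01 lacks the limit to intermediate doses found in C1.02, so its literal wording could reach them. But someone off treatment has not received incorrect medication, and SAP 7.3 counts compliance only up to discontinuation. This is a reason to state the limit, not evidence of a planned exclusion.

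The assumed shares are also open to challenge. Injections are given at the site by trained staff, so partial dosing may be rare.

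**Conclusion.** The contradiction between Protocol 7.2.1 and C2.01 is established from the text and needs no assumption. The treatment-dependent exclusion holds on the more natural reading of an undefined term, and is confined to partial under-dosing at attended visits.

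Its size cannot be derived from the documents. The 0.2-3 points shown rest on assumed shares and deficits, and on every under-dosed active patient having missed drug. They are an upper bound on that basis, not an estimate.

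A reader might infer that the primary result or the proof-of-concept decision is biased. It is not: both rest on the full analysis set, which C2.01 does not touch. What is weakened is the PPS as a robustness check, which justifies a correction before the Week 16 lock but does not threaten the trial's conclusion.

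**What to change.** Redefine C2.01 on blinded data, with the same rule in every arm. Flag a visit before Week 16, up to treatment discontinuation, if either:

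- a recorded medication number differs from the one assigned by IRT, or
- the number of syringes injected differs from the number planned for that visit.

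Settle it at the blinded meeting before the Week 16 lock. The data are already collected: "Each syringe will have an individual medication number for dispensation", and "Site personnel will enter the medication numbers in the eCRF". Syringe counts are recorded for compliance.

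After unblinding, list any patients whose actual content differed from plan and leave the main PPS unchanged. A PPS that also excludes them can be shown as a labelled supplementary analysis. If the sponsor prefers to keep a code-dependent rule, the minimum is to declare the departure in SAP Section 4, define the planned total dose, and make the rule mechanical and neutral between arms.

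The cost is SAP wording and one programmed check. There are two downsides. Swaps between syringes of identical content will be flagged. Wrong-content syringes dispensed as assigned will be listed but will not remove the patient from the main PPS.
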